4.3.5 Serious adverse reactions and unexpected adverse reactions

Definitions

Adverse Reaction: all untoward and unintended responses to an investigational medicinal product related to any dose administered.

Unexpected adverse reaction: an adverse reaction, the nature or severity of which is not consistent with summary of product characteristics for Truvada® (http://www.ema.europa.eu/docs/no_NO/document_library/EPAR_-_Product_Information/human/000594/WC500043718.pdf).

Suspected Unexpected Serious Adverse Reaction (SUSAR): any serious adverse reaction that might be related to the study medication and is unexpected according to the definition above.

4.3.6 Reporting of suspected unexpected serious adverse reactions by Investigator

Suspected unexpected serious adverse reactions (SUSARs) will be reported by the investigator according to appropriate Competent Authority and Ethics Committee requirements. SUSAR reporting to the Competent Authorities and Ethics Committees will be performed in writing using CIOMS forms, according to local regulations.

Fatal and life-threatening SUSARs should be reported as soon as possible to the Competent Authorities and Ethics Committees according to local regulations, and in any case no later than seven calendar days, after knowledge by Investigator of such a case. Relevant follow-up information on the case will be subsequently communicated within an additional eight days. All other SUSARs shall be reported to the Competent Authorities concerned and to the Ethics Committee concerned according to local regulations as soon as possible but within a maximum of fifteen days of first knowledge by Investigator.

In addition to the first evaluation of an adverse event that is performed by the investigator, a second evaluation with respect to seriousness, causality and expectedness and a risk-benefit assessment is performed by ISCR to process safety evaluation according to a four-eye principle.

5 INVESTIGATIONAL MEDICINAL PRODUCT

5.1 Investigational Medicinal Product and Comparator

The following medication supplies will be used in the study:

IMP:

Truvada® 200 mg/245 mg film-coated tablets. Each film-coated tablet contains 200 mg of emtricitabine and 245 mg of tenofovir disoproxil (equivalent to 300 mg of tenofovir disoproxil fumarate or 136 mg of tenofovir).

Excipients

Tablet core:

Croscarmellose sodium, Lactose monohydrate, Magnesium stearate (E572), Microcrystalline cellulose (E460), Pregelatinised starch (gluten free).

Film-coating:

Glycerol triacetate (E1518), Hypromellose (E464), Indigo carmine aluminium lake (E132)
Lactose monohydrate, Titanium dioxide (E171).

Marketing authorisation holder and manufacturer:

Gilead Sciences Intl Ltd. Cambridge CB21 6GT, UK

After the study protocol was sent to The Regional Committees for Medical and Health Research Ethics (REC South East), a parallel generic combination tablet (Emtricitabine/tenofovir disoproxil Sandoz®) became available in Norway. REC South East has been informed about this in an amendment.

Marketing authorisation holder and manufacturer of Emtricitabine/tenofovir disoproxil Sandoz®:

Sandoz A/S, [name], Danmark

Subject included in the control group will not receive any study specific treatment.

5.2 Supply, Packaging, Labelling, Handling and Storage

The subject will receive a prescription on FTC/TDF 200 mg/245 mg for a maximum of 3 months that will be collected at a regular pharmacy.

Labelling will be done by the pharmacy according to the prescribed dose and local regulations.

The subject will bring their remaining medication to the next visit to the clinic for the investigator to verify the used number of tablets.

The subjects will report their intake of medication in a paper diary received at the clinic or by an app on their phone (Viedocme). The subject should bring their paper diary to the clinic for every visit. In addition, plasma levels of either tenofovir or emtricitabine or both will be measured on every visit for those subjects enrolled for continuous PrEP as an objective tool to assess compliance.

5.3 Dosage and Administration

The subjects are enrolled in this study because they will receive FTC/TDF as PrEP treatment. FTC/TDF has a marketing approval in Norway and will be prescribed by the investigator as continuous treatment in accordance with the SmPC or intermittently according to the regime in the IPERGAY-study (ref) and The National Guidelines for the management and prevention of HIV.

Dosing continuous treatment: 1 tablet per day

Dosing intermittent treatment: 2 tablets 2-24 hours prior to sexual contact, and 1 tablet 24 and 48 hours after sexual contact, but max. 15-20 tablets per month. If in need of more tablets per month, national guidelines recommend continuous PrEP.

In accordance with the SmPC each subject will together with their physician decide whether they will take FTC/TDF every day or intermittent (on demand). Adherence should be closely followed during the study period.

Patients with a contraindication to FTC/TDF as a result of e.g. renal dysfunction, will be assessed according to standard of care. These patients may be referred to the Dept. of Infectious Diseases, Oslo University Hospital, for second opinion and may be included in this study if put on FTC/TDF, but not if offered an alternative regimen.

The subjects should be informed that PrEP treatment does not give full protection against HIV and offers no protection against other bacterial STIs and therefore should be used in combination with condom.

5.4 Duration of Treatment

Subject will be followed up for a period of up to 24 months.

5.5 Methods for Assigning Subjects to Treatment

There is no randomisation in this study. The subject will be prescribed PrEP as continuous or intermittent treatment as agree with the investigator according to their needs.

5.6 Concomitant Medication

Any medication (prescription as well as over the counter (OTC) drugs) or therapeutic intervention deemed necessary for the subject, and which, in the opinion of the Investigator, do not interfere with their safety, may be continued unless they are listed in 4.5 Interaction with other medicinal products and other forms of interaction of the SmPC.

Any medications, herbal medicines, natural health remedies and nutritional supplements used at Screening until Follow-up visit (24 months) are to be recorded in the Concomitant medication module in the eCRF system. The generic name of the medication (i.e., not local trade names), along with start date, stop date, dose, route, regimen and indication shall be recorded as applicable in the eCRF system.

Any new medications or changes to the dose or regimen of pre-existing medications will be updated on a routine basis during the study.

5.7 IMP Accountability

Medication will be prescribed on a reimbursable prescription and collected at their regular pharmacy. Subject will bring their remaining tablets to the clinical visits for the clinic to verify their compliance.

6 VARIABLES

- Demographic information (age, gender, race, height, weight, sexuality, education, work situation, relationship status)
- Sexual behaviour (number of partners, condom use, HIV positive partners)
- Sexual transmittable infections (history and current status for infections with syphilis, hepatitis A/B/C, *Chlamydia trachomatis*, *Neisseria gonorrhoea*, and *Mycoplasma genitalium*).
- Compliance (days tablets taken, days tablets missed, compliance (%), compliance in connection with exposure to infection, reason for poor compliance, serum concentration of FTC/TDF).
- HIV infection status (positive, negative, resistance)
- Quality of Life using attached questionnaire
- Adverse reaction related to PrEP treatment

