		
alcohol use.
 
Subject will be screened for the following STIs during the enrolment visit: HIV, syphilis, hepatitis A/B/C, Chlamydia trachomatis, Neisseria gonorrhoea, and Mycoplasma genitalium.
 
Participants will be asked to return approximately one week later to discuss their HIV result and whether they wish to proceed with initiation of PrEP.
 
The decision regarding initiation of continuous or intermittent PrEP is based on a discussion with the subject and study team (doctor/nurse), subjects' personal preference, medical considerations and whether the expected use will surpass more than 15-20 tablets of FTC/TDF per month.
 
HIV testing will be repeated at 2, 4 and 8 weeks from the most recent high risk exposure (for HIV acquisition) prior to initiation of PrEP. Thereafter participants are requested to visit the clinic every 3 months from PrEP initiation (for the next 24 months) for HIV & STI testing, evaluation of compliance (blood test for drug monitoring in continuous PrEP arm, drug diaries in both continuous and intermittent PrEP arms), assessment of clinical and/or biochemical adverse reactions and quality of life and sexual behaviour assessment. Subjects will be asked to answer the same questions regarding sexual behaviour and quality of life at follow up visits as at inclusion study visit.

Statistics	Sample size	Not applicable
	Methods	Categorical variables will be described by means of absolute and relative frequencies, while continuous variables by means of mean, standard deviation, quartiles, min and max.

LIST OF ABBREVIATIONS

AE	Adverse Event
ART	Anti retroviral therapy
COHP	Country of high prevalence of HIV
CRA	Clinical Research Associate
CRF	Case Report Form
CSR	Clinical Study Report
CT	Chlamydia trachomatis
DM	Data Manager
EC	Ethics Committee
eCRF	Electronic Case Report Form
EDC	Electronic Data Capture
EMA	The European Medicines Agency
GCP	Good Clinical Practice
HIV	Human Immunodeficiency Virus
ICF	Informed Consent Form
ICH	International Conference on Harmonisation
IMP	Investigational Medicinal Product
ISF	Investigator Site File
ITT	Intention-To-Treat
MG	Mycoplasma genitalium
MSM	Men who have sex with men
NG	Neisseria gonorrhoea
PI	Principal Investigator
PIS	Patient Information Sheet
PrEP	Pre-Exposure Prophylaxis
SAE	Serious Adverse Event
SD	Standard Deviation
SDV	Source Data Verification
SUSAR	Suspected Unexpected Serious Adverse Reaction
STI	Sexually Transmitted Infections

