4.2 Variables

Subjects will be treated according to local prescribing information and clinical judgement and assessments performed according to site clinical practice. The inclusion period will last from final approval from The Regional Ethical Committee and until end of 2018.

Data on demographics, sexual health including sexual behaviour, HIV infection status, STIs, compliance and recreational drug use will be collected at the baseline visit, 3 months' follow-up visits, end of study visit and relevant extra visits. HIV-tests will also be taken at weeks 2, 4 and 8 in order to identify people in the seroconversion phase at inclusion to reduce risk of development of drug resistance. For subjects at particular high risk for HIV infection prior to PrEP treatment, HIV-DNA provirus testing will be assessed at the first visit according to the doctor's clinical judgement. As a measure of adherence blood samples will be drawn and the tenofovir disoproxil fumarate (TDF) concentration in plasma will be measured as well as a self-reported drug protocol.

Investigators are asked to report the requested data in the electronic Case Report Form (eCRF).

Table 1 Data collection and visit structure

Study Visits ¹	Visit 0 (evaluation)	Visit 1(start of treatment)	Visit 2 (week 2)	Visit 3 (week 4)	Visit 4 (week 8)	Follow-up visits (approx. every 3 months)	Extra visits	End of study visit (24 months after start of treatment)
Clinic visits	x			x		x ¹	x	x
Informed consent	X							
Assess eligibility criteria	x	x						
Demography	X							
HIV test ²	x		x	x	x	x	x ³	x
HIV-DNA provirus ⁴	x ⁴	x ⁴						
History of STI	x							
STI screening	x					x	x ³	x
Bloodsample for TFV-PD plasma concentration				x		x ⁵	x ^{3,5}	x ⁵
Questionnaire sexual behaviour (start of treatment)	x					x		x
Questionnaire sexual behaviour (follow-up)	x					x		x
Compliance				x		x	x	x
Adverse events				x		x	x	x
Subject diary				x		x		x

¹ clinic visits to be schedule to fit with PrEP treatment guidelines and local clinical practice. At each visit assessments as indicated in table should be captured in the database if they are conducted.

² If a subject is infected with HIV during PrEP treatment resistance of the HIV virus for emtricitabine and tenofovir disoproxil fumarate should be checked.

³ If clinically indicated

⁴ If high risk sexual contact within the last 14 days

⁵ only applicable for subject on continuous PrEP treatment

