7.3 Descriptive statistics

Categorical variables will be described by means of absolute and relative frequencies, while continuous variables by means of mean, standard deviation, quartiles, min and max. Analyses will consider data collected at variable observational points, according to clinical practice and clinical judgement. In order to summarize data by time point the nearest available evaluation measurement will be considered (acceptable range).

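### Plasma drug levels serve as a compliance check, but neither document specifies recording dose and draw times, and the week-4 cell of Table 1 conflicts with the outline and section 5.2 on who is sampled

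*Protocol*

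**What the plan says.** Drug compliance is one of five study objectives. Protocol section 4.2 states: "As a measure of adherence blood samples will be drawn". It adds that the concentration "will be measured as well as a self-reported drug protocol". Section 5.2 describes the plasma level, taken at every visit in continuous users, as an objective check on compliance. Sections 5.2 and 5.7 also have subjects bring remaining tablets to be counted, and section 5.2 provides a paper or app diary of intake. Under compliance, section 6 lists counts of days with and without tablets and percentage compliance, followed by "compliance in connection with exposure to infection, reason for poor compliance, serum concentration of FTC/TDF".

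On who is sampled, the outline assigns "blood test for drug monitoring in continuous PrEP arm, drug diaries in both continuous and intermittent PrEP arms". In the Table 1 sampling row, the follow-up, extra-visit and end-of-study cells carry footnote 5: "only applicable for subject on continuous PrEP treatment". The week-4 cell carries no footnote.

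On analysis, section 7.3 summarises "continuous variables by means of mean, standard deviation, quartiles, min and max". It has no rule for time since dose, no concentration threshold and no split by regimen. Section 7.1 defers detail to a separate SAP. The SAP supplied repeats that sentence, the same Table 1 cells and the same section 7.3.

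**The concern.** A plasma concentration falls from one tablet to the next, so a single value depends on the hours since the last dose as well as on whether earlier doses were taken. The diary and the tablet count depend on what the subject reports or brings back. The level is the only laboratory check on compliance, and it can be interpreted only if the dose-to-draw interval is known. If that interval is not captured at the visit, it may not be recoverable after database lock. Two visits, sites or groups could then show different average levels with identical compliance, or similar levels with different compliance.

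The week-4 cell adds a second difficulty at one visit. A fully compliant intermittent user may have taken no tablet for days, so a low level there says little about compliance.

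**Working it through.** The plan states no figure to reproduce: the sample size entry is "Not applicable" and no half-life, assay limit or threshold is given. The check sets the passages side by side and then sizes the timing and regimen effects.

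**1. What is sampled, and in whom**

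| Place (protocol) | Users sampled | Analyte and matrix |
|---|---|---|
| Outline | continuous arm | not named |
| 4.2, text | no limit by regimen | TDF, plasma |
| Table 1, week 4 | no footnote, so all users | TFV-PD, plasma |
| Table 1, later visits | continuous only (footnote 5) | TFV-PD, plasma |
| 5.2 | continuous, every visit | tenofovir, emtricitabine or both, plasma |
| 6 | no limit by regimen | FTC/TDF, serum |

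The week-4 cell is the same in the SAP's Table 1, so a text-extraction fault is unlikely. No row of Table 1 and no item in section 6 asks for the time of last dose or of draw.

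**2. Timing in daily users**

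Input from the documents: one tablet per day (section 5.3). Assumptions: single-exponential decline at steady state, with half-life *h* of 10 to 24 h; 30 h is added as a stress case. With dosing interval τ, the level *t* hours after a tablet is proportional to 2^(−t/h) / (1 − 2^(−τ/h)).

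- A: full compliance, 2 h versus 24 h after a tablet = 2^(22/h).
- B: full compliance versus alternate-day dosing, both drawn at 2 h = (1 − 2^(−48/h)) / (1 − 2^(−24/h)) = 1 + 2^(−24/h).
- C: alternate-day user at 2 h versus fully compliant user at 24 h = A / B.

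| h (hours) | A | B | C |
|---|---|---|---|
| 10 | 4.59 | 1.19 | 3.86 |
| 15 | 2.76 | 1.33 | 2.08 |
| 20 | 2.14 | 1.44 | 1.49 |
| 24 | 1.89 | 1.50 | 1.26 |
| 30 | 1.66 | 1.57 | 1.06 |

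At *h* = 10, for example, A = 2^2.2 = 4.59, B = 1 + 2^(−2.4) = 1.19, and C = 4.59 / 1.19 = 3.86. In this example, someone missing every second tablet can read higher than someone missing none, clearly at short half-lives and barely at 30 h.

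**3. Regimen at week 4**

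Inputs from section 5.3: four tablets per episode (two taken 2 to 24 h before contact, one each at 24 and 48 h after) and a cap of 15 to 20 tablets a month. An episode therefore spans 2 + 48 = 50 h to 24 + 48 = 72 h, and the cap allows 15/4 = 3.75 to 20/4 = 5 episodes. Assumptions: a 30-day month (720 h), episodes that do not overlap, and a randomly timed draw.

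- At 3.75 episodes: 3.75 × 50/720 = 26% to 3.75 × 72/720 = 38% of the month is inside an episode.
- At 5 episodes: 5 × 50/720 = 35% to 5 × 72/720 = 50%.
- At 1 episode: 50/720 = 7% to 72/720 = 10%.

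Counting a further 24 h after the last tablet raises these to 39–50%, 51–67% and 10–13%. A fully compliant intermittent user is thus outside a dosing episode for at least half the month, and for about 90% or more of it at one episode a month.

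**The case against.** The strongest reply is that the level is one of several measures. The diary, the tablet count and the days taken or missed cover the whole interval between visits, and no stated test or decision rule uses the concentration in this descriptive study. That stands, and it limits the consequence: compliance would not rest on the level alone.

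The fields of the diary, questionnaires and eCRF are not in the documents. A reader might infer that dose times will not be recorded; the documents show only that recording them is not specified. The diary may yield at least a date.

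A reader might also infer that week-4 samples from both regimens will be pooled, or that regimen distorts levels throughout. Pooling is stated nowhere. The regimen problem comes from one cell and affects one visit, since every later cell is limited to continuous users.

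Finally, a reader might conclude that levels reflect timing more than compliance. The documents cannot show this. The comparison above depends on an assumed half-life and on one pattern of missed doses, and it nearly vanishes at 30 h. It does not consider complete stopping, which a level detects best. Nor does a later clinic hour necessarily lower the level, because that depends on when each subject takes the tablet.

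What remains after these limits is that the times, an interpretive rule and a single analyte are unspecified, and that the week-4 cell conflicts with other text.

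**Conclusion.** The point holds in a limited form. Under the plan as written, a summary of plasma levels cannot separate dose-to-draw timing from adherence. Timing alone can change a fully compliant daily user's reading by a factor of about 1.9 to 4.6, if the half-life is 24 to 10 h and decline is single-exponential between 2 and 24 h. These factors illustrate scale. The half-life is not a figure from the documents, and no one value can apply until the analyte is fixed.

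The week-4 conflict needs no outside figure. Table 1 as printed includes intermittent users, while the outline and section 5.2 describe drug monitoring for continuous users only. The unrestricted wording of section 4.2 means the missing footnote cannot simply be taken as a slip.

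This is worth correcting because the level is the plan's only laboratory check on a stated objective and the missing times may not be retrievable later. It does not invalidate the compliance assessment as a whole.

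**What to change.** 1. Add to the eCRF, at each concentration sample, the date and time of the last tablet and the date and time of the draw. For samples already taken, use any dose dates the diary holds and otherwise report the interval as missing.
2. Reconcile the week-4 cell of Table 1 with the outline and section 5.2, in both documents. Report any samples from intermittent users separately.
3. Name one analyte and one matrix, and use them consistently in sections 4.2, 5.2 and 6 and in Table 1.
4. In the SAP, replace the single summary of levels with one by regimen and time since last dose. Describe it as evidence of recent dosing, alongside diary and tablet-count compliance.

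The cost is two eCRF fields, one reconciled cell, consistent naming and one changed table. Classifying subjects as having dosed recently or not would need a concentration threshold by time since dose. The documents supply none, so that would be additional work and is not needed for this correction.

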7 STATISTICAL METHODOLOGY AND DATA MANAGEMENT

7.1 Statistical Analysis Plan

All analyses will be performed by the Sponsor after the study is completed and the database is locked. Statistical programming and analyses will be performed using SAS and/or other validated statistical programs. A detailed statistical analysis plan (SAP) will be described in a separated document.

7.2 Study Populations

Data will be described on enrolled subjects undergoing PrEP treatment. Subjects who do not satisfy inclusion criteria will not be included in the analysis. A summary table reporting reasons for exclusion will be provided.

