3 POPULATION

3.1 Inclusion Criteria

In order to participate in the PrEP arm of this study the subjects must meet all of the following inclusion criteria:

1. Male, female or transgender persons aged ≥ 18 years who are offered or have started PrEP in routine clinical practice, and 2, 3, 4, 5, 6 or 7 (below).
2. Men who have sex with men (MSM) and transgender persons;
 - a. who have had unprotected anal sex with two or more partners during the last six months and/or
 - b. who have had bacterial sexually transmittable infection(s) during the last twelve months and/or
 - c. who have used post-exposure prophylaxis(PEP) during the last twelve months and/or
 - d. who use recreational drugs when having sex
3. Indication for PrEP is present according to the assessment of the health care provider
4. Men and women who are at high risk of HIV according to their sexual practices
5. HIV-negative partner of a HIV-positive person not yet virologically suppressed by antiretroviral therapy (ART)
6. Sex workers with inconsistent condom use
7. Persons with inconsistent condom use with sexual partners in / from countries with a high prevalence of HIV (COHP)

Subjects who are included in the PrEP arm will act as their own controls regarding possible changes in psychological and sexual health. At the screening visit they will complete questionnaire requesting information related to last 6 months prior to study start. Individuals who seroconvert during the observational period will be transferred to the out-patient clinic for Infectious Diseases as is already standard of care.

Patients diagnosed with HIV in general clinical practice and referred to the out-patient clinic at the Dept. of Infectious Diseases, OUS, will be asked to act as controls to assess their past psychological and sexual health. They will be asked to sign the consent form and answer the same questionnaire as those in the PrEP arm but not followed further in this study.

Frequency of STI reported to the National Institute of Public Health (MSIS) will be compared with the frequency of STIs in the study cohort.

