3.4 Recruitment and Screening

Individuals attending the clinic for PrEP assessment are either referred from other health care providers or referred by themselves (self-referral).

Those who have commenced PrEP elsewhere (abroad, purchased themselves, another provider) and attend for "PrEP follow-up" either at Olafiaklinikken or a corresponding venereological clinic/study site in Norway, may also be included in the study.

Eligible subjects will have the study explained to them, and will receive the written informed consent form (ICF). After having had the time to review the nature of the study, they will have the opportunity to ask questions to the investigating team. If the subject agrees to participate, they will be asked to sign and date one original written informed consent form (ICF). The subject will then receive a copy of the signed and dated patient information/informed consent form. The original signed ICF will be filed in the Investigator Site File (ISF). The PIS will contain site contact information in case of any questions or medical emergency.

Newly diagnosed HIV positive individuals referred to the out-patient clinic of the Dept. of Infectious Diseases, OUS, will be invited to participate as controls. The inclusion and exclusion criteria for the control group aim at including newly infected individuals (< 12 months) residing in a country for > 6 months where PrEP might have been available, and excluding individuals infected long time ago in a country where PrEP was inaccessible; i.e. mostly countries with high HIV-prevalence outside the EU/EFTA-region, North America and Australia/New Zealand. They will be presented with the same consent form and questionnaire on sexual and psychological health prior to the HIV diagnosis.

Any written information given to potential subjects will be submitted to, and approved by, the Ethics Committee(s) prior to implementation.

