4 TREATMENT PROCEDURES

4.1 Study plan

The observation will begin after the subjects have signed the informed consent form. PrEP treatment should then be initiated when the HIV antibody/antigen test (4th generation test) taken at the first visit is confirmed negative.

However, the window period to rule out HIV infection is 12 weeks. It is not desirable that participants are undergoing HIV seroconversion when they commence PrEP, however the study population is per definition at high-risk for HIV acquisition. It is likely that the majority of the participants will not be in a position to abstain from sex or use condoms effectively for a 12 week period. Therefore it is NOT recommended to delay PrEP pending a negative HIV test results 12 weeks from the last high risk exposure. International and national guidelines do not recommend delaying PrEP initiation in this high risk group for HIV acquisition. Per definition, those in need for PrEP are at high risk for HIV acquisition justifying PrEP initiation even at first visit.

For those who have had high risk exposure within 14 days prior to screening, a HIV-DNA provirus test should be requested and the serum test for HIV should be repeated at 2 weeks, 4 weeks and 8 weeks and 12 weeks from the day they commenced PrEP.

Subjects that have already commenced PrEP treatment can be included in the study. These subjects will be requested to consent to collection of historical medical information from the date when the PrEP treatment was initiated.

Follow-up visits are according to clinical practice, clinical judgement and standard patient management described in SmPC. For those outside the window period for HIV infection a standard visit at 4 weeks and 12 weeks post initiation of PrEP and thereafter every 3 months during the PrEP treatment for 24 months. Where clinically indicated the subject may attend the clinic between 3 months' follow-up visits. Data from these visits will be collected as Extra Clinical Visits.

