4.3 Adverse Events and Serious Adverse Events

4.3.1 General

The Investigator should ask the subject questions during the clinic visits in order to ensure that appropriate adverse event information is recorded in the subject's source notes and is then subsequently entered into the CRF. Adverse events will be recorded in response to the following question - "Since you were last asked have you felt unwell or different from usual in any way?" All relevant responses from the subject will be recorded in the CRF on an adverse

event form and graded on severity, seriousness and relationship to study medication. For further details regarding the classification of adverse events see below.

Subjects will be questioned regarding any signs and symptoms occurring in the screening period and for baseline signs and symptoms prior to the first dose of study medication on Day 1. Subjects will subsequently be questioned regarding adverse events throughout the study. All adverse events are to be reviewed by the Investigator while on-going and subsequently documented at the point of resolution. All adverse events classified as serious are to be immediately brought to the attention of the Investigator by site staff for review and action in accordance with Section 4.4.5 below.

All on-going adverse events will be followed up by the Investigator until subject discharge or resolution. Additional clinic visits may be scheduled by the Investigator to follow-up on adverse events according to their clinical judgement.

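### Adverse reactions are pooled over starters and established PrEP users, so the frequency is expected to understate that in people starting PrEP, by an amount the documents do not fix

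*Protocol*

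**What the plan says.** **Who may enrol.** Inclusion criterion 1 (section 3.1) admits adults "who are offered or have started PrEP in routine clinical practice". Section 3.4 extends recruitment to people who began PrEP abroad, bought it themselves or had it from another provider. Section 4.1 confirms it: "Subjects that have already commenced PrEP treatment can be included in the study". No limit on the length of earlier use is given. Section 4.1 also asks these subjects to consent to collection of their medical history back to the start of PrEP.

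**What is analysed, and on whom.** Section 6 lists "Adverse reaction related to PrEP treatment" as a variable. Section 7.2 defines the population: "Data will be described on enrolled subjects undergoing PrEP treatment". Section 7.3 gives the summary: "Categorical variables will be described by means of absolute and relative frequencies". It also provides for summaries by time point, using the nearest available measurement. Section 7 has no split by prior use, no time since first tablet and no person-time.

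**How events are captured.** Observation begins at consent (section 4.1). Table 1 first schedules adverse events at week 4, then at the three-monthly, extra and end-of-study visits. The question put to subjects is "Since you were last asked have you felt unwell or different from usual in any way" (section 4.3.1). That section also asks about signs and symptoms at baseline, before a first dose on Day 1.

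The SAP carries the same provisions in sections 3.1, 3.4, 4.1, 4.3.1, 6, 7.2 and 7.3, and adds no split.

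**The concern.** The analysis set mixes two kinds of subject. For a starter, the study sees the first tablet and what follows. An established user has already passed through the early period, and is there to be enrolled only because PrEP was not abandoned. Someone who began elsewhere and stopped because of a reaction has no reason to attend for PrEP follow-up and does not enter the denominator or the numerator.

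Capture differs as well. The prospective question reaches back only to the previous enquiry. No study visit precedes an established user's true first dose, so a drug effect already present at enrolment could be recorded as a baseline symptom.

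If the pooled percentage is taken as what a person starting PrEP can expect, it is likely to be too favourable. It would also depend on how many established users happened to enrol.

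**Working it through.** The plan states no sample size, reaction frequency, stopping rate or share of established users, so there is no figure to reproduce. Every input below is an assumption. The calculation shows what the size depends on and does not estimate it.

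**Step 1: general form.** Let
- p = reaction frequency in starters
- f = share of established users in the analysis set
- r = counted reaction frequency in established users divided by p

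Pooled frequency = (1 − f)p + f·r·p = p[1 − f(1 − r)].

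| f | r | Multiplier | Reported if p = 20% |
|---|---|---|---|
| 20% | 0.5 | 1 − 0.2 × 0.5 = 0.90 | 18.0% |
| 30% | 0.3 | 1 − 0.3 × 0.7 = 0.79 | 15.8% |
| 50% | 0 | 1 − 0.5 × 1 = 0.50 | 10.0% |
| any | 1 | 1 | 20.0% (no bias) |

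The last assumed pair (f = 50%, r = 0) is extreme. It needs every established user to have no counted reaction of any grade throughout follow-up.

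**Step 2: include the medical history under section 4.1.** Suppose all reactions occur early. Let d = share of reactors who stop before they could enrol, and h = share of the remaining established users' early reactions recovered from history.

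Frequency among established users still on PrEP = p(1 − d)/(1 − pd).

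Reported frequency = (1 − f)p + f·h·p(1 − d)/(1 − pd).

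With p = 10%, d = 50%, f = 30%, the frequency among remaining users is 0.05/0.95 = 5.26%, and:
- full history (h = 1): 7.0% + 0.3 × 5.26% = 8.6%
- half (h = 0.5): 7.0% + 0.3 × 0.5 × 5.26% = 7.8%
- none (h = 0): 7.0%

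Over p = 5–20%, d = 25–50% and f = 10–50%, the relative shortfall is:

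| History recovered | Shortfall |
|---|---|
| all | 2–24% |
| half | 6–37% |
| none | 10–50% |

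In this model, complete history reduces the shortfall but does not remove it when d is above zero, because history cannot reach people who never enrolled.

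**Step 3: starters alone.** Setting f = 0 returns p, here 10.0%.

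**Step 4: what the models leave out.** Step 2 ignores reactions with late onset. Established users have longer total time on drug, so late reactions, including laboratory abnormalities, raise r and offset part of the shortfall. The documents give no timing from which to judge how much.

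**The case against.** The strongest reply is that reaction risk in people starting PrEP is not something this study sets out to estimate. None of the five objectives in section 2 concerns adverse reactions, which appear only in the variable list and among the planned visit assessments. The population is defined to include people already on PrEP, and a frequency over that population describes it correctly. This stands. A reader might infer that a stated objective is compromised. The documents do not support that; the bias arises only when the figure is read as the risk on starting.

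A second reply is that one ever/never percentage is inferred from general wording, and that summaries by time point might keep the early period apart. This stands in part. Table 1 dates the end-of-study visit from the start of treatment, but neither document says what that origin is for someone already on PrEP. The time-point rule therefore does not secure the separation.

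Third, the medical history and late reactions work against the shortfall. Both points hold for its size. The history provision depends on consent, does not name adverse reactions, has no row in Table 1 and no rule in section 7.

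Fourth, section 7.1 promises a detailed SAP in a separate document. The SAP supplied repeats that sentence and the protocol's analysis text, so on the documents available there is no split.

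**Conclusion.** The point holds as an expectation conditional on how the figure is used. Under sections 7.2 and 7.3, starters and established users are summarised together, with two risk periods and two ways of finding events. The resulting frequency is expected to understate that in people starting PrEP. This rests on three assumptions: some established users enrol, some people stop early because of a reaction, and late reactions do not make up the difference.

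The size cannot be derived. The ranges above follow from assumed inputs, and if established users have the same counted risk there is no bias.

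Three stronger readings should be avoided. One is that the percentage is certainly too low; the historical data and late reactions rule out that certainty. Another is that it is understated by as much as half; that needs half the set to be established users with no counted reactions. The third is that a planned comparison between sites is lost; no such comparison is planned. This is a cheap improvement to the analysis, and no stated objective depends on it.

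**What to change.** In section 7.2 or 7.3 of both documents, report adverse reactions separately for:

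- **(a)** subjects starting PrEP for the first time at or after enrolment
- **(b)** subjects already on PrEP at consent
- **(c)** former users restarting PrEP, who fit neither of the other groups

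Present (a) as the frequency for people starting PrEP. For (b), count only events with onset after consent, measure time on PrEP from the initiation date, and list reactions from the historical record in a separate table. Confirm that the eCRF records the initiation date and prior use. Section 4.1 implies the date, but section 6 and Table 1 do not list it as a field.

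This changes the analysis only: a few sentences and one table split, with all subjects still reported. The cost is a smaller denominator for the starter frequency. If 30% of the set were outside group (a), and the frequency itself were unchanged, its standard error would rise by a factor of 1/√0.7 = 1.20. At 50% the factor is 1/√0.5 = 1.41. Section 7.3 plans no intervals, so no planned analysis is lost.
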